### **Exclusion criteria**

- Age younger than 18 years;
- Secondary causes of glaucoma (e.g., iridocyclitis, trauma);

STU00213080

- Any evidence of corneal or conjunctival pathology adjacent to filtration bleb that could influence AS-OCT image
- Patients who did not undergo surgery or have adequate follow up
- Adults unable to consent, individuals who are not yet adults (infants, children, teenagers), pregnant women, prisoners and vulnerable populations

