**STUDY ENDPOINTS:**

STU00213080

Results from the following tests obtained as part of this study:

1. Spectralis Anterior-segment OCT (AS-OCT) (Heidelberg Engineering) available in Lavin 15th floor Ophthalmology clinic
2. Digital microscope integrated with Intraoperative OCT (Zeiss Artevo 800, Carl Zeiss Meditec AG) available in the Lavin 11th floor operating room

The primary outcome will be surgical success, defined as a 20% reduction in unmedicated IOP below the pre-operative baseline at the post-operative visits (POD1, POM1, POM3). The success rate will be compared to a cohort of historical controls comprised of a consecutive series of age- and race-matched subjects who underwent TCNR in the operating room by the same surgeon, with the same intraoperative anti-fibrotic therapy, without AS-OCT or iOCT imaging during a five-year time period from 6/1/2015 to 6/1/2020.

The secondary outcomes will be feasibility and utility of intraoperative OCT. Feasibility will be defined as the percentage of cases with successful imaging of the bleb with iOCT. Utility will be defined as the percentage of cases in which iOCT changed surgical decision-making.

Intraoperative OCT will be used to determine whether adhesions have been completely lysed and/or whether further lysis of adhesions is necessary. A survey with set of questions based on prior literature will be used to assess these parameters.

We will also assess whether findings seen with pre-operative AS-OCT can predict what type of blebs will benefit from iOCT-assisted TNCR. Features of AS-OCT and iOCT imaging that will be assessed include quality of image capture, visualization of surgical site, and characteristics of the bleb. Characteristics of the surgical site include bleb height, internal reflectivity, location and number of adhesions, and presence of cysts, cavities, and fistulas.

STU00213080

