**PROCEDURES INVOLVED:**

The devices used in the study are commercially available and have been used extensively in ophthalmology and intraocular surgery. Therefore, no experimental devices will be used. The AS-OCT is routinely obtained and is considered standard of care. The iOCT is commercially available and is also utilized routinely in ophthalmic surgery, particularly for retinal surgery.

The Zeiss Artevo digital microscopy integrated with intraoperative OCT will be used as an adjunct to TCNR. Published research has not shown iOCT to increase risk of complications associated with routine TCNR and we believe injury from imaging is not biologically plausible. Surgery and iOCT will be recorded and saved to a secure NMH server. The surgical videos will only be used for research purposes.

Review of medical records will be performed for patients who agree to participate in the prospective study. Data gathered will include basic demographic information and clinical data relevant to glaucoma management (visual acuity, intraocular pressure, medications, disease

STU00213080

severity). Post-operative course including intraocular pressure, intraoperative or post-operative complications and repeat TCNR or additional surgery will also be collected.

Furthermore, a retrospective review of medical records will be performed for patients who underwent TCNR without iOCT or AS-OCT assistance by the same surgeon during the period from June 1, 2015 to June 1, 2020. This group of patients will serve as historical controls. These individuals will be identified using Enterprise Data Warehouse and billing data. We aim to identify approximately 25 controls. The selection criteria for controls are 1) age within 5 years of each study patient 2) same race as study patient 3) diagnosis of open angle glaucoma and 4) adequate follow up of at least 3 months.

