### **COMPENSATION FOR PARTICIPATION IN RESEARCH ACTIVITIES**

There is no additional cost for the patient to participate in this study. Patients and their insurance companies will be billed for office visits and procedures that are part of their usual medical care. There is no compensation made to the study subjects for participating in this study. Patients will have routine preoperative and postoperative follow up visits as necessary based on their clinical course. No extra visits will be required as a result of participation in this study.

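### Eligibility depends on follow-up that is known only after the operation, which could bias the success rate in either group

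*Protocol*

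**What the plan says.** Two places in the Protocol make inclusion conditional on what happens after surgery.

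- Exclusion criteria: the list removes "Patients who did not undergo surgery or have adequate follow up". No duration is attached. The list is not labelled by group, but its items on consent and imaging show that it is written for the prospective patients.
- PROCEDURES INVOLVED: the fourth selection criterion for controls is "adequate follow up of at least 3 months".

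Four other sections bear on this.

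- STUDY ENDPOINTS judges the primary outcome, a 20% fall in unmedicated pressure from baseline, at POD1, POM1 and POM3. It describes the controls as a "consecutive series of age- and race-matched subjects who underwent TCNR in the operating room by the same surgeon".
- RECRUITMENT METHODS says that invitations go only to patients who meet the criteria.
- COMPENSATION FOR PARTICIPATION IN RESEARCH ACTIVITIES says: "Patients will have routine preoperative and postoperative follow up visits as necessary based on their clinical course". It adds that taking part requires no additional visits.
- STUDY TIMELINES plans 12 months of follow-up for participants.

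**The concern.** An eligibility criterion has to be decidable when the patient enters. Whether follow-up was adequate is settled only weeks or months after TCNR, so the criterion cannot screen anyone at invitation. It can only take eyes out afterwards, when their outcome may already be partly or wholly known.

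That matters if attendance is related to outcome. An eye doing well might stop attending, or an eye doing badly might be managed elsewhere. The two would push the observed success rate in opposite directions. In the controls the filter reaches exactly to the last primary-outcome visit, so a control counts only if it was still under observation when its outcome was complete. If success is meant to hold at every listed visit, a control that missed the target at POD1 or POM1 and then left is already a known failure, yet the rule makes it ineligible instead of counting it.

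This is separate from voluntary withdrawal, which has its own section: the rule also removes patients who never withdrew. For controls the loss is permanent. An eye rejected at chart review never enters the dataset, so no later analysis can bring it back.

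**Working it through.** **1. When each criterion can be decided.**

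| Criterion | Where | Decidable |
|---|---|---|
| Age, race, diagnosis | PROCEDURES INVOLVED; inclusion and exclusion lists | Before TCNR |
| Underwent surgery | Exclusion criteria | On the day of TCNR |
| Adequate follow-up, no figure | Exclusion criteria | Some unstated time after TCNR |
| Follow-up of 3 months or more | PROCEDURES INVOLVED, controls | 3 months after TCNR |

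The last two rows cannot be met or failed when a patient is invited. This conflicts with RECRUITMENT METHODS, under which only patients meeting the criteria are approached.

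**2. Overlap with the outcome.** The last primary visit is at 3 months and the control filter is 3 months. The filter therefore covers the whole outcome window.

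**3. The Protocol's own figures.** It plans 25 prospective and about 25 control eyes. It gives no expected success rate, no loss rate and no count of eyes screened out. There is nothing to reproduce, and every figure below rests on assumed inputs. With 25 eyes in a group, one eye is 1/25 = 4 percentage points.

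**4. Bounds on what the filter can hide (assumed counts).** With n eyes retained, s successes among them and m eyes screened out, the rate among all operated eyes lies between s/(n+m) and (s+m)/(n+m). Take n = 25 and s = 15, so the reported rate is 15/25 = 60%.

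- m = 0: 60%, no effect.
- m = 5: 15/30 = 50% to 20/30 = 66.7%.
- m = 10: 15/35 = 42.9% to 25/35 = 71.4%.

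These are extremes, with every removed eye a failure or every one a success. They are not estimates of bias.

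**5. Selection under assumed retention.** Let p be the true success rate, and rS and rF the shares of successes and failures that pass the filter. The observed rate is p·rS / [p·rS + (1−p)·rF]. With p = 0.50:

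- rS = rF: 50%, no bias.
- rS = 0.95, rF = 0.80: 0.475/0.875 = 54.3%.
- rS = 0.95, rF = 0.70: 0.475/0.825 = 57.6%.
- rS = 0.90, rF = 0.60: 0.45/0.75 = 60.0%.
- The same patterns reversed: 45.7%, 42.4% and 40.0%.

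So these patterns shift one group's rate by about 4 to 10 points, either way.

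**6. Effect on the comparison.** If both groups are filtered alike, most of the shift cancels in the difference. With true rates of 40% and 60% and retention of 0.95 and 0.70 in both groups, the observed rates are 0.38/0.80 = 47.5% and 0.57/0.85 = 67.1%, a difference of 19.6 points against a true 20. Each rate is still about 7 points too high. If only one group is filtered and both true rates are 50%, a two-sided pooled z test at 5% with 25 per group (an assumed test, enumerated exactly) rejects with probability 7.7%, 10.3% or 13.1% when the filtered group shows 54.3%, 57.6% or 60.0%. With no filtering it rejects 6.5% of the time.

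**The case against.** The other side has several good points, and they limit how far this can be taken.

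- **Stronger selection in the controls.** A reader might infer that prospective patients are kept under observation by consent while controls have only the visits that their course produced. The documents do not show this. The statement that visits follow the clinical course describes the study participants, and participation adds no visits. The planned 12 months hints at a difference but does not establish one. Similar filtering in both groups would largely cancel in the difference.
- **Bias as a fact.** Nothing says that eyes doing well are discharged early or that failing eyes leave. The filter is on duration, not outcome, and an eye needing a repeat TCNR by the same surgeon could easily reach 3 months. Only the possibility of bias is supported.
- **Two standards.** A reader might conclude that the groups face different follow-up rules. The same phrase appears in both places, and the control section gives it a figure that matches the last primary visit. A missing figure in one list is a drafting gap, not proof of two standards.
- **A false claim of consecutiveness.** The endpoint section speaks of consecutive matched subjects, which can mean consecutive among those eligible. Controls are also chosen by "age within 5 years of each study patient" and by race, so they were never going to be every operated eye. This is a point of wording.
- **Analysis-plan content.** Handling of missing POM3 pressures may sit in a statistical analysis plan that is not shown. That is fair, and its absence is not part of this point. The eligibility and control-selection rules, however, are fixed in the Protocol.

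None of this removes the core: inclusion is conditioned on post-operative follow-up in both places.

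**Conclusion.** The point stands in limited form. The Protocol uses follow-up known only after TCNR as an eligibility rule, and gives it a figure only for controls. For controls the rule spans the whole primary-outcome window; for prospective patients it can act only as a later removal. It could bias the success rate in either group. Its size, its direction and whether it differs between groups cannot be determined from the documents. The shifts of 4 to 10 points, the 50% to 67% bounds and the rejection rates show what assumed losses could do; they are not estimates for this trial. The conclusion rests on the text and on one assumption, that attendance may be related to how the eye is doing. If it is unrelated, the rates are not biased, but the removed eyes should still be counted and reported. The change should be made because it is cheap and because rejected controls cannot be recovered later.

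**What to change.** - In Exclusion criteria, delete the follow-up half of the item. The half about not undergoing surgery can stay, because it is settled on the day of TCNR.
- In PROCEDURES INVOLVED, delete the fourth control criterion ("adequate follow up of at least 3 months").
- State that eligibility in both groups is defined by facts known on or before the day of TCNR, and that controls are selected by surgery date, matching and baseline criteria only.
- Keep every eligible operated eye in the primary denominator. Make clear in the participant tables that the 25 per group are eligible operated eyes, not eyes with complete follow-up.
- Report by group how many eyes lack a POM3 pressure. As a supporting analysis, show the success difference with those eyes counted as failures and then as successes.
- In STUDY ENDPOINTS, reword the description of the controls as consecutive among eligible matched eyes, and give the number screened out.

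The cost is Protocol wording and one short table, with no new visits. The downside is that some control eyes will have missing POM3 pressures and the reported range will be wider.

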**VULNERABLE POPULATIONS: NONE****PARTICIPANT POPULATION(S)**

## Prospective Study Population

Accrual Number:	Category/Group: (Adults/Children Special/Vulnerable Populations)	Consented: Maximum Number to be Consented or Reviewed/Collected/Screened	Enrolled: Number to Complete the Study or Needed to Address the Research Question
Local	25 adults	25 adults	25 eyes
Study-wide			
Total:	25 adults	25 adults	25 eyes

## Age and race matched historical controls (identified via retrospective chart review)

Accrual Number:	Category/Group: (Adults/Children Special/Vulnerable Populations)	Consented: Maximum Number to be Consented or Reviewed/Collected/Screened	Enrolled: Number to Complete the Study or Needed to Address the Research Question
-----------------	---	---	--

STU00213080

Local	25 adults	0	25 eyes
Study-wide			
Total:	25 adults	0	25 eyes

### **RECRUITMENT METHODS**

Potential participants will be identified from the patients scheduled for follow up in the Glaucoma Service at Northwestern Medicine. Potential participants who are already scheduled for surgery may be called to gauge interest in the study. If they express interest, the patient will return to clinic prior to surgery to review and sign the informed consent and complete pre-surgery study imaging. Only patients who fit the inclusion/exclusion criteria will be asked to participate in the study.

### **COMPENSATION FOR PARTICIPATION IN RESEARCH ACTIVITIES**

There is no additional cost for the patient to participate in this study. Patients and their insurance companies will be billed for office visits and procedures that are part of their usual medical care. There is no compensation made to the study subjects for participating in this study. Patients will have routine preoperative and postoperative follow up visits as necessary based on their clinical course. No extra visits will be required as a result of participation in this study.

### **WITHDRAWAL OF PARTICIPANTS**

All the participants are free to withdraw at any point of the study. In case the participants are not willing to continue with the study protocol they will be removed from the analysis.

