## **STUDY TIMELINES**

STU00213080

The participant will be in the study for the duration of their office visit (with AS-OCT testing) and surgery. In the context of this research study, participants will also be followed for 12 months after surgery to assess their post-operative course.

It will likely take approximately 12 months to enroll all study participants. The estimated date for completion of primary analyses will be 6 months after enrollment of study.

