#### **CONSENT PROCESS**

Potential participants in the prospective study will be identified from the patients scheduled for follow up or surgery in the Glaucoma Service at Northwestern Medicine. Patients will be approached verbally about the study during their visits or over the phone by study approved personnel. The informed consent process will take place in person in a private room. The research team will go over the consent forms with the patients to ensure they understand the nature of the research study, its procedures, potential risks and benefits, and their responsibilities as participants. The patients will be given as much time as needed to consider the study and address any questions or concerns. If patients need additional time to decide whether or not to enroll in the study, they will have the option of rescheduling for a later time.

STU00213080

Throughout the consent process, the research team will stress that participation is completely voluntary and that participants may withdraw from the study at any point. Patients will be provided a copy of the fully executed, signed consent forms. An additional copy of the signed consent forms will be scanned into the patient's electronic medical record and hard copies will be maintained in the subject binder.

For the historical control data, a retrospective chart review of glaucoma patients who underwent TCNR surgery from June 1, 2015 to June 1, 2020, will be performed. Consent will not be obtained for these patients as they will not undergo any further testing or treatments.

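### The withdrawal rule excludes operated eyes from analysis with no time limit, losing feasibility and utility results fixed at surgery and, after month 3, a complete primary outcome

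*Protocol*

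**What the plan says.** The section Withdrawal of Participants has two sentences: "All the participants are free to withdraw at any point of the study", and then "In case the participants are not willing to continue with the study protocol they will be removed from the analysis". Neither sets a time limit, and neither says what happens to data already recorded.

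Four other parts of the protocol bear on the rule:

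- **Endpoints.** Study Endpoints defines the primary outcome as a 20% fall from baseline in IOP off medication "at the post-operative visits (POD1, POM1, POM3"). Feasibility is the share of cases in which iOCT imaged the bleb successfully. For the other secondary outcome, "Utility will be defined as the percentage of cases in which iOCT changed surgical decision-making". The intervention section places iOCT imaging at the beginning and end of the operation.
- **Follow-up.** Under Study Timelines, "participants will also be followed for 12 months after surgery to assess their post-operative course".
- **Controls.** Consent Process says of the historical controls: "Consent will not be obtained for these patients as they will not undergo any further testing or treatments". Procedures Involved admits a control only with at least 3 months of follow-up.
- **Numbers.** The table for the prospective population gives a maximum of 25 adults consented. Under "Enrolled: Number to Complete the Study or Needed to Address the Research Question" it gives 25 eyes.

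**The concern.** A withdrawal after surgery cannot change whether the bleb was imaged or whether iOCT altered a decision in theatre. Dropping such a case from the feasibility and utility percentages discards valid information for no gain. After month 3 the same holds for the primary outcome, because its visits are complete.

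For the primary comparison the issue is selection. If the choice to stop is related to how the eye is doing, removing those eyes shifts the prospective success rate. If patients doing badly stop more often, success is overstated; if patients doing well lose interest, it is understated. No control can leave by this route once the outcome is known. A confidence interval computed on the remaining eyes would not show the shift.

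**Working it through.** **Inputs from the protocol.** 25 prospective eyes and about 25 controls; primary visits to month 3; follow-up to month 12; about 12 months to enrol; primary analysis 6 months after enrolment. The protocol gives no success rate, withdrawal rate, significance level or power, so the figure of 25 cannot be re-derived. The success, utility and withdrawal counts below are assumptions.

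**Step 1: what is already recorded when a participant stops.**

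| Time of stopping | Already recorded | Effect of the rule |
|---|---|---|
| Before surgery | No outcome | Nothing lost; not at issue |
| Surgery to month 3 | Feasibility, utility, perhaps the day 1 and month 1 visits | Secondary results lost; primary outcome incomplete in any case |
| Month 3 to month 12 | Feasibility, utility and all primary visits | All of it excluded |

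**Step 2: length of the window after the last primary visit.** 12 − 3 = 9 months, and 9/12 = 75% of follow-up. This is a share of calendar time, not a risk of withdrawal. Assume that the primary analysis is timed from the end of enrolment and that surgery follows enrolment closely. The last patient enrolled then has 6 − 3 = 3 of those months before the analysis. The first has 12 + 6 = 18 months of elapsed time, which exceeds 12, so all 9.

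**Step 3: how far removal can move a rate.** With s successes among 25 eyes and w removed, the observed rate lies between (s − w)/(25 − w), if all removed eyes are successes, and s/(25 − w), if all are failures.

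| Assumed rate | Remove 1 | Remove 3 | Shift with 3 removed |
|---|---|---|---|
| 10/25 = 40% | 9/24 to 10/24: 37.5% to 41.7% | 7/22 to 10/22: 31.8% to 45.5% | −8.2 to +5.5 points |
| 15/25 = 60% | 14/24 to 15/24: 58.3% to 62.5% | 12/22 to 15/22: 54.5% to 68.2% | −5.5 to +8.2 points |
| 20/25 = 80% | 19/24 to 20/24: 79.2% to 83.3% | 17/22 to 20/22: 77.3% to 90.9% | −2.7 to +10.9 points |

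The control rate is unchanged, so the difference between arms moves by the same amount. The first row also serves for utility at an assumed 40%.

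**Step 4: comparison with random error.** Treating the arms as independent with 25 each and 60% in both, the 95% margin on the difference is 1.96 × √(2 × 0.6 × 0.4 / 25) = 1.96 × 0.139 = 0.272, or about ±27 points. The shifts in Step 3 lie inside it, and their extremes require all removed eyes to share one outcome.

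**Step 5: room for replacement.** Maximum consented minus number needed is 25 − 25 = 0. A removed eye cannot be replaced within that ceiling.

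**The case against.** The strongest reply is that the rule hardly reaches operated eyes. Study Timelines opens by describing participation as the clinic visit with AS-OCT plus the operation. The compensation section adds no visits beyond routine care, and Procedures Involved takes the post-operative course from medical records. Little is left after surgery for a participant to decline, so the rule may have been meant for people who refuse imaging or surgery. This stands as a limit on the likely number of eyes. It does not remove the point: the next sentence of Study Timelines puts 12 months of follow-up within the study, and the withdrawal rule carries no limit by timing.

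A second reply is that the controls are also selected for completeness, through the 3-month follow-up criterion. This stands too. Leaving prospective eyes that stop before month 3 out of the primary comparison resembles what is done to the controls, which narrows the asymmetry to eyes removed after month 3.

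A third is that a statistical analysis plan may define the analysis sets. One that kept these eyes would contradict an explicit protocol sentence, so the sentence needs changing either way.

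A reader might also infer that records are destroyed, or that every withdrawal loses month-3 data. The documents support neither. The rule concerns the analysis only, and month-3 data are at stake only for those who stop after that visit.

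**Conclusion.** The rule is explicit and badly fixed. As written, it excludes feasibility and utility results already settled at surgery and, for withdrawals between months 3 and 12, a finished primary outcome. In the primary comparison the one-sided effect is mainly this late removal of prospective eyes whose outcome is known.

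Severity is minor to moderate. The illustrated shifts, up to about 11 points with 3 eyes removed, rest on assumed rates and on the most extreme pattern of removal, and they are smaller than the random error. A reader might conclude that the comparison is biased in favour of iOCT. The document does not support that: it gives no withdrawal rate and no link between stopping and outcome, so neither direction nor size can be stated.

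**What to change.** 1. **Replace the removal sentence** in Withdrawal of Participants with text to this effect: *Data collected up to withdrawal are kept and analysed unless the participant withdraws permission for their use; otherwise only participants who stop before surgery are left out.*
2. **Feasibility and utility:** compute both on all operated eyes in which iOCT was attempted, whatever the later follow-up, subject to the same permission.
3. **Primary comparison:** keep every operated eye whose primary visits through month 3 are recorded, even if the participant withdraws later. Treat eyes without a month-3 visit by the same follow-up rule as the controls. Report the number and timing of withdrawals.

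A separate eligibility inconsistency should be settled in the same amendment. The exclusion list contains "Patients who did not undergo surgery or have adequate follow up". Adequate follow-up is defined only for controls, under Procedures Involved, and cannot be known when Recruitment Methods applies the criteria to prospective patients. The three sections must be reconciled, stating which arm the criterion covers.

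**Cost.** These are wording changes, with no extra patients or visits. The reported success rate may be less favourable. The consent wording on keeping data, which is not shown, must agree with the new sentence. If the common follow-up rule differs from the present control criterion, the matched controls must be rechecked.
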